#### 9.2.5 Digital Biomarker Analyses

Digital biomarker data will be analyzed for: a) participant adherence; b) agreement between participant/caregiver reports and behavioral data; c) dependence on age and IQ and difference from TD healthy participants.

 Since digital biomarker data is collected at home, participant and caregiver compliance is an important measure of the success of the approach. Participant adherence will be determined by both completion of daily tasks (surveys and active

- tests) and use of the wearable, which can be tracked with sensors that are built into the device.
- b) The passive monitoring approaches will be analyzed for agreement with participant/caregiver reports. The focus of the analyses will be on repetitive movements, patterns of movement around the home and beyond, and heart rate signals as these relate to anxiety.

Dependence of the digital biomarker assessment on age and IQ and difference to typical developing controls will be explored.

Further details of planned analyses will be provided in the technical document.

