#### NUMBER OF PARTICIPANTS

Approximately 90 participants with ASD will be enrolled into six cohorts with approximately 15 participants each. The six cohorts are defined by all combinations of the below categories for the two factors ABIQ and age:

- ABIQ: participants with ABIQ ≥ 70 vs participants with ABIQ ≥ 50 and < 70.

- Age: children 5 to 12 years; adolescents 13 to 17 years and adults 18 to 45 years.

In addition, 45 TD healthy participants (15 children age 5 to 12 years, 15 adolescents age 13 to 17 years, and 15 adults age 18 to 45 years) will be enrolled for validation of digital biomarkers only.

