Stanford Binet (SB-5) abbreviated IQ test 	Х						
Incl/Excl criteria	Х						
Demography	Х						
Identification of targeted behaviors for app	Х						
Hand over devices and training	Х						
dBM run-in to validate devices and apps	←						
RMET 		Х				Х	Х
Digital Biomarker Collection		-					
Phone contacts 			X β	Х	Х		
Return devices and satisfaction survey 5						Х	Х
Adverse Events 	-						-

Digital biomarkers will be collected from all participants, those with ASD and the *typically developing (TD)* healthy participants.

- 1. Clinical visits can be performed over 2 days.
- 2.A Stanford-Binet Intelligence scales test up to 12 month old is acceptable.
- 3. Follow-up by telephone will include questions about participant's welfare and progress in collection of digital biomarker data.
- 4. The RMET will provide anchor data for analysis of digital biomarkers and will be conducted also in *TD* healthy participants. An age specific version of the RMET will be completed as deemed appropriate by Investigator for details (see Table 4).
- 5. Final satisfaction surveys on the participant's experience about collection of digital biomarker will be completed by participants *and by caregivers*.
- 6. For all participants with ASD at week 2 a mandatory clinic visit will be completed. For the *TD* healthy participants at week 2 a telephone contact will be sufficient.
- 7. Only adverse events and serious adverse events caused by a protocol-mandated intervention should be reported see Section 8.3.

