### 4.2.1 Rationale for Study Population

Children, adolescents and adults (aged 5-45 years) with clinical diagnosis of ASD according to DSM-5 criteria and confirmed by Autism Diagnostic Observational Schedule (ADOS-2) will be enrolled. The lower age limit (5 years) will allow building a significant database from broad pediatric population. Although data suggest that the diagnosis of ASD is possible below the age of 5, the diagnosis is less reliable and may not be stable, and as a consequence will be excluded from this trials, although younger participants may be included in future trials.

Participants with at least moderate ASD symptoms and current presence of RRBs will be recruited to allow the monitoring of these behaviors during the study. To this aim, only participants with a Clinical Global Impression-severity (CGI-S)  $\geq$  4 (at least moderately-ill) and a Children's Yale-Brown Obsessive Compulsive Scale in Autism Spectrum Disorder (CY-BOCS-ASD) total score of at least 12 at screening will be enrolled. Participants with a low intelligence quotient (IQ) below 50 (Stanford-Binet Intelligence Scales 5th edition Abbreviated Battery Intelligence Quotient scale (ABIQ) will be excluded because of the higher prevalence of significant co-morbidities in this population.

Since there is wide consensus that the nature and intensity of RRBs depend on age and IQ, participants will be recruited into six cohorts of 15 participants to ensure enough variance across these two factors. Cohorts will be stratified firstly on ABIQ (participants who have an ABIQ  $\geq$  70 versus participants who have an ABIQ  $\geq$  50 and < 70), and secondly based on age (children, adolescents and adults; see Section 5).

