## 4.2.2 Rationale for Control Group

This study includes a group of TD healthy male and female participants (15 children age 5 to 12 years, 15 adolescents age 13 to 17 years, and 15 adults age 18 to 45 years). The TD healthy participants will be needed to compare and validate the digital biomarkers versus participants with ASD. The TD healthy control group will participate in collection of digital biomarker data (see Schedule of Activities [SoA] for digital biomarkers, Table 2) and except of the Reading the Mind in the Eyes Test (RMET) needed as anchor data for the analysis of digital biomarkers, no clinical scales will be performed in the TD healthy control group since these scales are not suitable for typically developed individuals (see main SoA, Table 1).

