# Inclusion criteria specific to typically developing healthy participants:

1. Male and female TD healthy participants age 5 to 45 years inclusive.

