# 9.2.4 Statistical methods for the Secondary Objectives

The effect of age and IQ on RRBs in subjects with ASD will be evaluated with graphical displays and by applying regression models with the RRB scale as dependent and age and IQ and other possible covariates

The correlation structure between scales will be evaluated by means of multivariate methods such as principal component analyses and factor analyses

All listed p-values will be interpreted only as descriptive weights and not in a confirmatory sense.

Further details of planned analyses will be provided in the technical document.

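### Does the exploratory comparison of digital biomarkers between ASD and typically developing participants need a stated rule for handling IQ?

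*Combined protocol and SAP*

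**What the plan says.** Section 9.2.5 lists three analyses of the digital biomarkers: adherence, agreement between reports and sensor data, and a third item that names IQ and age dependence together with the TD difference. The closing text repeats that pairing: "Dependence of the digital biomarker assessment on age and IQ and difference to typical developing controls will be explored". It then defers: "Further details of planned analyses will be provided in the technical document".

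The groups are built differently. The synopsis (Number of Participants) and Section 9.1 divide about 90 ASD participants into six cohorts of about 15, by three age bands and by "participants with ABIQ ≥ 70 vs participants with ABIQ ≥ 50 and < 70". The 45 TD participants are recruited at 15 per age band. Section 5.1 requires of them specifically only "Male and female TD healthy participants age 5 to 45 years inclusive", Section 5.2 excludes those with a first-degree relative with ASD, and the ABIQ criterion stands under the ASD-only heading.

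Section 9.2.4 does name IQ in a model, but for the RRB scales in ASD participants: "regression models with the RRB scale as dependent and age and IQ and other possible covariates".

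On whether IQ is measured in TD participants, Table 2 (Section 1.2), which covers everyone, lists at screening "Stanford Binet (SB-5) abbreviated IQ test". Section 4.2.2 states that, apart from the RMET, "no clinical scales will be performed in the TD healthy control group", and Table 4 includes the SB5 in its overview of clinical scales.

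**The concern.** Section 4.2.2 gives the TD group its purpose: comparing and validating the digital biomarkers against ASD. If half of one group has an ABIQ below 70 by design and the other group has hardly anyone there, a raw group difference carries the IQ gap with it. Spatial working memory and emotion recognition, both digital endpoints in Table 3, plausibly depend on IQ. For repetitive behaviour the protocol itself opens its cohort rationale in Section 4.2.1 with "Since there is wide consensus that the nature and intensity of RRBs depend on age and IQ". Section 9.2.4 puts IQ in the regression for the scales, while Section 9.2.5 says nothing equivalent about the TD contrast.

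At stake is whether a difference on an IQ-dependent measure could be read as specific to autism, in a study meant to inform later drug trials. Any IQ adjustment also needs ABIQ from TD participants, and Section 4.2.2, read literally with Table 4, could suggest that it is not collected.

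**Working it through.** **The plan's own figures.** ASD: 6 × 15 = 90. TD: 3 × 15 = 45. Low-ABIQ share of ASD: 3 × 15 / 90 = 45/90 = 50%. These reproduce. Section 9.1 says the sample size was not based on power, so there is no power figure to check.

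**Overlap in IQ.** Assume TD IQ is normal with mean 100 and SD 15 (not in the documents). Then P(IQ < 70) = Φ(−2) = 0.0228, and 45 × 0.0228 is about 1 TD participant, against about 45 ASD participants. The groups would barely overlap in the low stratum.

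**Size if the contrast were pooled and unadjusted.** Assumptions, none from the documents: TD mean 100, ASD means 60 and 95 in the two strata, SD 15, no autism effect, and the same IQ slope in both groups.
- ASD mean = (60 + 95)/2 = 77.5, so the gap is 100 − 77.5 = 22.5 points.
- Spurious difference d = r × gap/15, where r is the correlation of the measure with IQ.
- SE = √(1/90 + 1/45) = 0.183. P is the two-sided chance of nominal p < 0.05 by the normal approximation.

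| r | d (gap 22.5) | P | P over gaps of 20 to 25 |
|---|---|---|---|
| 0 | 0 | 5% | 5% |
| 0.1 | 0.15 | 13% | 11% to 15% |
| 0.2 | 0.30 | 38% | 31% to 45% |
| 0.3 | 0.45 | 69% | 59% to 78% |
| 0.5 | 0.75 | 98% | 95% to 99.5% |

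Gaps of 20 and 25 correspond to a high-stratum ASD mean of 100 and 90. An SD of 15 cannot hold inside a 50-to-69 stratum, where the maximum is 9.5 and a uniform spread gives about 5.8. Using 5.8 there changes P at r = 0.3 only from 69% to 68%.

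**What an ABIQ ≥ 70 contrast would buy and cost.** With 45 against 45, SE = √(2/45) = 0.211, up from 0.183. With a residual gap of 5 points, d is 0.03 to 0.17 and P is 5% to 12% for r = 0.1 to 0.5. With a gap of 10 and r = 0.5, d = 0.33 and P = 35%. The difference detectable with 80% power at two-sided 0.05 (both assumed) is 2.80 × SE, which rises from 0.51 to 0.59 SD. Restriction removes much of the bias but not all of it, and it costs precision and half of the ASD group.

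**What the text commits to.** No section specifies a pooled, unadjusted contrast. Section 9.2.5 sets IQ dependence beside the TD difference for the same measures and leaves the model to the technical document. The table therefore describes a choice that the plan does not make.

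**Whether ABIQ is collected in TD participants.** Table 2 gives the SB-5 its own row and footnote and omits the ADOS-2 and CY-BOCS-ASD, so it is not a copy of the ASD schedule. Section 4.2.2 sends the reader to Table 2 for TD procedures. Its reason for leaving out scales is that they do not suit typically developed people. That reason does not fit the SB5, which Section 8.1.1.4 describes as a general test of cognitive abilities and intelligence. The likely reading is that ABIQ is collected in TD participants and that Section 4.2.2 is loosely worded.

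**The case for a change.** The strongest argument for a change is that confounding biases the estimate itself, so calling a result exploratory or a p-value descriptive does not remove it. Examining IQ dependence also does not commit anyone to adjusting or restricting the TD contrast. Because few TD participants would fall below 70, adjustment over the full range would extrapolate, which makes the form of the comparison worth naming. The technical document is not available here, so it cannot be shown to settle the matter. And a site that followed Section 4.2.2 literally could omit the IQ test, which could not readily be recovered later.

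The statistical reasoning stands: a naive pooled contrast would mislead for an IQ-dependent measure. It does not show that the plan calls for one. An analyst who has to report IQ dependence for each biomarker, in a study with cohorts defined by ABIQ, will see the problem and has the strata to deal with it.

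The obvious remedy, a main contrast confined to ABIQ ≥ 70, is open to dispute. It removes half of a group recruited deliberately across the IQ range. Showing the TD contrast by ABIQ stratum beside the pooled result would serve an exploratory aim equally well. The wording of Section 4.2.2 remains untidy, but the schedule it points to is clear.

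**Conclusion.** No change to the plan follows. Section 9.2.5 leaves out detail on an exploratory comparison; it does not state an analysis that gives a wrong answer. The 50% low-ABIQ share and the lack of a TD IQ criterion are facts of the documents. The possible bias, 0 to 0.75 SD for correlations of 0 to 0.5, rests wholly on assumed IQ means, SD and correlations, and on a pooled, unadjusted contrast that no section prescribes. So wide a range shows that confounding is possible, not how large it would be.

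The digital objectives are tertiary or exploratory in Table 3. The protocol's statement that p-values are descriptive appears in Section 9.2.4, and no test threshold is set for the digital measures. Agreement with participant and caregiver reports and the RMET anchor also bear on validation, so only the interpretation of this one contrast is in play. The conclusion assumes that ABIQ is collected in TD participants as Table 2 schedules, and that the analysts use it when they read the TD difference.

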### 9.3 SUMMARIES OF CONDUCT OF STUDY

All protocol deviations will be listed. Data for concomitant medication will be listed. The number of participants who were enrolled, discontinued and completed the study will be summarized and listed.

# 11. SUPPORTING DOCUMENTATION AND OPERATIONAL CONSIDERATIONS

The following section includes standard appendices: Appendix 1 (for regulatory, ethical and study oversight considerations), Appendix 2 (for AE definitions, reporting). Additional study-related appendices are in order of appearance in the protocol.

# Appendix 1 Regulatory, Ethical, and Study Oversight Considerations

# 1. REGULATORY AND ETHICAL CONSIDERATIONS

#### 1.1. COMPLIANCE WITH LAWS AND REGULATIONS

This study will be conducted in full conformance with the ICH E6 guideline for Good Clinical Practice and the principles of the Declaration of Helsinki, or the laws and regulations of the country in which the research is conducted, whichever affords the greater protection to the individual. The study will comply with the requirements of the ICH E2A guideline (Clinical Safety Data Management: Definitions and Standards for Expedited Reporting). Studies conducted in the United States or under a U.S. Investigational New Drug (IND) application will comply with U.S. FDA regulations and applicable local, state, and federal laws. Studies conducted in the EU/EEA will comply with the EU Clinical Trial Directive (2001/20/EC).

#### 1.2. INSTITUTIONAL REVIEW BOARD OR ETHICS COMMITTEE

This protocol, the ICFs, any information to be given to the participant (e.g., advertisements, diaries etc), and relevant supporting information must be submitted to the IRB/EC by the Principal Investigator and reviewed and approved by the IRB/EC before the study is initiated. In addition, any participant recruitment materials must be approved by the IRB/EC.

The Principal Investigator is responsible for providing written summaries of the status of the study to the IRB/EC annually or more frequently in accordance with the requirements, policies, and procedures established by the IRB/EC. Investigators are also responsible for promptly informing the IRB/EC of any protocol amendments (Section 2.3.1 of this Appendix).

The Investigator should follow the requirements for reporting all adverse events (as specified) to the Sponsor. Investigators may receive written IND safety reports or other safety-related communications from the Sponsor. Investigators are responsible for ensuring that such reports are reviewed and processed in accordance with Health Authority requirements and the policies and procedures established by their IRB/EC, and archived in the site's study file.

#### 1.3. INFORMED CONSENT/ ASSENT FORMS

The Sponsor's Master Informed Consent Form (and ancillary sample ICFs such as a Child's Assent or Caregiver's Informed Consent Form, if applicable) will be provided to each site. If applicable, it will be provided in a certified translation of the local language. Participants must be informed that their participation is voluntary. Participants or their legally authorized representative (guardian or caregiver) will be required to sign a statement of informed consent that meets the requirements of 21 CFR 50, local regulations, ICH guidelines, Health Insurance Portability and Accountability Act

requirements, where applicable, and the IRB/IEC or study center. The Sponsor or its designee must review and approve any proposed deviations from the Sponsor's sample ICFs or any alternate consent forms proposed by the site (collectively, the "Consent Forms") before IRB/EC submission. The final IRB/EC-approved Consent Forms must be provided to the Sponsor for Health Authority submission purposes according to local requirements. A copy of the ICF(s) signed by all parties must be provided to the participant's legally authorized representative.

The Consent Forms must be signed and dated by the participant or the participant's legally authorized representative before his or her participation in the study. The case history or clinical records for each participant shall document the informed consent process and that written informed consent was obtained prior to participation in the study.

The Consent Forms should be revised whenever there are changes to study procedures or when new information becomes available that may affect the willingness of the participant to take part. The final revised IRB/EC-approved Consent Forms must be provided to the Sponsor for Health Authority submission purposes if required as per local regulations.

Participants must be re-consented to the most current version of the Consent Forms (or to a significant new information/findings addendum in accordance with applicable laws and IRB/EC policy) during their participation in the study. For any updated or revised Consent Forms, the case history or clinical records for each participant shall document the informed consent process and that written informed consent was obtained using the updated/revised Consent Forms for continued participation in the study.

A copy of each signed Consent Form must be provided to the participant or the participant's legally authorized representative. All signed and dated Consent Forms must remain in each participant's study file or in the site file and must be available for verification by study monitors at any time.

Participants who are re-screened are required to sign a new ICF.

#### 1.4. CONFIDENTIALITY

Participants will be assigned a unique identifier by the Sponsor. Any participant records or datasets that are transferred to the Sponsor will contain the identifier only; participant names or any information which would make the participant identifiable will not be transferred.

The participant must be informed that his/her personal study-related data will be used by the Sponsor in accordance with local data protection law. The level of disclosure must also be explained to the participant.

Medical information may be given to a participant's personal physician or other appropriate medical personnel responsible for the participant's welfare, for treatment purposes.

The participant must be informed that his/her medical records may be examined by Clinical Quality Assurance auditors or other authorized personnel appointed by the Sponsor, by appropriate IRB/IEC members, and by inspectors from regulatory authorities.

#### 1.5. FINANCIAL DISCLOSURE

Investigators will provide the Sponsor with sufficient, accurate financial information in accordance with local regulations to allow the Sponsor to submit complete and accurate financial certification or disclosure statements to the appropriate Health Authorities. Investigators are responsible for providing information on financial interests during the course of the study and for one year after completion of the study (i.e., LPLO).

# 2. DATA HANDLING AND RECORD

#### 2.1. DATA COLLECTION AND MANAGEMENT RESPONSIBILITIES

# 2.1.1. Data Quality Assurance

All participant data relating to the study will be recorded on electronic CRF unless transmitted to the Sponsor or designee electronically (e.g., scales data). The Investigator is responsible for verifying that data entries are accurate and correct by physically or electronically signing the CRF.

The Investigator must maintain accurate documentation (source data) that supports the information entered in the CRF.

The Investigator must permit study-related monitoring, audits, IRB/IEC review, and regulatory agency inspections and provide direct access to source data documents.

The Sponsor or designee is responsible for the data management of this study including quality checking of the data.

Study monitors will perform ongoing source data verification to confirm that data entered into the CRF by authorized site personnel are accurate, complete, and verifiable from source documents; that the safety and rights of participants are being protected; and that the study is being conducted in accordance with the currently approved protocol and any other study agreements, ICH GCP, and all applicable regulatory requirements.

### 2.1.2. Clinical Outcome Assessment Data

#### 2.1.2.1 Electronic Clinical Outcome Assessment Data

Participants will use an eCOA device to capture COA data. The data will be transmitted electronically to a centralized database at the eCOA vendor. Entries should be reviewed for completeness during the clinic visit.

eCOA data will be collected using an electronic device provided by an eCOA vendor. The device is designed for entry of data in a way that is attributable, secure, and accurate, in compliance with U.S. Food and Drug Administration (FDA) regulations for electronic records (21 CFR Part 11). System backups for data stored by the Sponsor and records retention for the study data will be consistent with the Sponsor's standard procedures.

# 2.1.3. Preexisting Medical Conditions

A pre-existing medical condition is one that is present at the screening visit for this study. Such conditions should be recorded on the General Medical History and Baseline Conditions eCRF.

# 2.1.4. Source Data Records

Source documents (paper or electronic) are those in which participant data are recorded and documented for the first time. They include, but are not limited to, hospital records, clinical and office charts, laboratory notes, memoranda, COAs (paper or eCOA), evaluation checklists, pharmacy dispensing records, recorded data from automated instruments, copies of transcriptions that are certified after verification as being accurate and complete, microfiche, photographic negatives, microfilm or magnetic media, X-rays, participant files, and records kept at pharmacies, laboratories, and medico-technical departments involved in a clinical trial.

Source documents that are required to verify the validity and completeness of data entered into the eCRFs must not be obliterated or destroyed and must be retained per the policy for retention of records described below.

To facilitate source data verification, the Investigators and institutions must provide the Sponsor direct access to applicable source documents and reports for trial-related monitoring, Sponsor audits, and IRB/EC review. The investigational site must also allow inspection by applicable Health Authorities.

